AE	Adverse event (see definition in Section 6.3.1)
AUC	Area under plasma concentration time curve from zero to infinity
AUC _(0-t)	Area under plasma concentration time curve from zero to last quantifiable time point
AUC ₍₄₋₈₎	Area under plasma concentration time curve from 4 to 8 hours postdose
%AUC _{ex}	Percentage of AUC obtained by extrapolation
BMI	Body Mass Index
BP	Blood pressure
CI	Confidence interval
CL/F	Apparent plasma clearance
CL _D	Dialysate clearance
Cl _R	Renal clearance
C _{max}	Maximum plasma concentration
CPA	Clinical Pharmacology Alliance
CRF	Case Report Form (electronic/paper)
CL _{CR}	Creatinine clearance
CSA	Clinical Study Agreement
CSP	Clinical Study Protocol
CSR	Clinical Study Report
C-SSRS	Columbia-Suicide Severity Rating Scale
CV%	Coefficient of variation (%)
DAE	Discontinuation of Investigational Product due to Adverse Event
DES	Data Entry Site
DMP	Data Management Plan
DMPK	Drug metabolism and pharmacokinetics
DNA	Deoxyribonucleic acid

Abbreviation or special term	Explanation
ECG	Electrocardiogram
ESRD	End stage renal disease
eCRF	Electronic case report form
eGFR	Estimated glomerular filtration rate
f_e	Fraction of dose excreted as unchanged drug into urine
$f_{d(4-8)}$	Fraction of dose extracted unchanged into the dialysate over the dialysis period from 4 hours postdose to 8 hours postdose
FSH	Follicle stimulating hormone
GCP	Good clinical practice
GMP	Good manufacturing practice
HIV	Human immunodeficiency virus
ICF	Informed Consent Form
ICH	International Conference on Harmonisation
IP	Investigational Product
IRB	Institutional Review Board
LIMS	Laboratory Information Management System
LH	Luteinizing hormone
LLOQ	Lower Limit of Quantification
MDRD	Modification of Diet in Renal Disease
OAE	Other Significant Adverse Event (see definition in Section 11.1.1)
pCRF	paper case report form
PGx	Pharmacogenetic research
PI	Principal Investigator
PK	Pharmacokinetics
PR(PQ)	ECG interval measured from the onset of the P wave to the onset of the QRS complex.
QRS	ECG interval measured from the onset of the QRS complex to the J point.
QT	ECG interval measured from the onset of the QRS complex to the end of the T wave
QTcF	QT interval corrected for heart rate using Fridericia's formula
RR	The time between corresponding points on 2 consecutive R waves on ECG
SAD	Single ascending dose
SAE	Serious adverse event (see definition in Section 6.3.2).

Abbreviation or special term	Explanation
SD	Standard deviation
SOP	Standard Operating Procedure

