2.2 Secondary objectives

- To assess the effect of hemodialysis on TC-5214 PK
- To assess the safety and tolerability of TC-5214 in subjects with renal impairment compared with those subjects with normal renal function

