admitted into the clinic the morning of Day -1, or on Day -2 at the discretion of the Investigator. Time-matched vital signs will be collected on Day -1. Subjects will receive a single dose of TC-5214 on Day 1 after completion of a dialysis session and will remain in the clinic for pharmacokinetic sample collections and safety assessments until the start of their next dialysis session. Subjects who are unable to remain in the clinic during this time may have their samples collected as outpatients. Subjects will return to the clinic after a washout period of at least 2 weeks to start Treatment Period 2. Subjects will be admitted to the clinic the morning of Day -1 or on Day -2 at the discretion of the Investigator for Treatment Period 2. Time-matched vital signs will be collected on Day -1. Subjects in Treatment Period 2 will receive a single dose of TC-5214 on Day 1, at 4 hours prior to the start of a dialysis session. Subjects will remain in the clinic until the start of their next dialysis session. Blood samples will be collected prior to dialysis, during the entire dialysis session, and until the start of their next dialysis session. Safety assessments will be performed periodically throughout the treatment period. Dialysis fluid will be collected in 1-hour intervals. Subjects who are unable to remain in the clinic through the entire treatment period may have their samples collected as outpatients. Subjects will return to the clinic for a follow-up visit 7 to 10 days following discharge from Treatment Period 2. Subjects who withdraw from the study after completion of Treatment Period 1 (assessments between dialysis) and before entering Treatment Period 2 (assessments during dialysis) may be replaced at the discretion of the Sponsor.

For details on Part 1, see the Study Flow Charts ([Figure 1](#) and [Figure 2](#)) and the Study Plan Table 1 below.

3.1.2 Part 2

3.1.2.1 Part 2, Groups 1 through 3

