3.2 Rationale for study design, doses and control groups

The purpose of this study is to determine if renal impairment will affect the PK of TC-5214. The study is designed using the principals embodied in the Food and Drug administration guidance on drug renal impairment studies ([Cockcroft 1976](#)).

For control subjects with normal renal function and subjects with mild renal impairment, a 8 mg dose of TC-5214 was chosen because it is the highest daily dose that will be administered in Phase III trials and was shown to be well tolerated in healthy subjects in previous studies. For subjects with moderate and severe renal impairment, to minimize the effects of compensatory changes such as significant hypotension, a 2 mg dose will be administered.

In order to avoid bias due to demographic differences between the control subjects with normal renal function and subjects with renal impairment, the control group will be matched to the mean demographic characteristics of the **3** renal impairment groups with an allowable variability in age of +/- 10 years and in BMI of $\pm 3 \text{ kg/m}^2$. Sex will be matched to achieve similar distribution between male and female subjects. Only control subjects with stable chronic medical conditions will be included.

Based on available data to date, the mean terminal half-life ($t_{1/2,\lambda_z}$) of TC-5214 in human plasma is approximately 8 to 9 hours. Based on limited interim PK data in 2 subjects with moderate impairment, and 2 subjects with ESRD, renal impairment has been shown to increase the half-life of TC-5214 by approximately 3 and 10 fold, respectively.

For Groups 1 to 3, the study design has been updated to extend the sampling period to 120 hours postdose to adequately characterize the elimination phase of TC-5214 and more accurately determine TC-5214 PK parameters (eg $t_{1/2,\lambda_z}$, AUC, and CL/F). For Group 5 it was determined that a single dose of TC-5214 administered after the completion of a dialysis session, with the collection of blood samples for PK through 120 hours postdose (including a 4 hour dialysis session beginning approximately 72 hours postdose) would enhance patient safety.

The PK profile in patients with severe renal failure will be extrapolated from the data in subjects on dialysis obtained between their dialysis sessions, thus subjects with severe renal impairment (eGFR <30 mL/min) will not be recruited for this study.

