6.4.1.1 Blood Samples

Blood samples (approximately 6 mL, split into 2 tubes, collected in K2 EDTA tubes) for determination of TC-5214 in plasma will be taken on the days presented in the study plans [Table 1](#) and [Table 2](#).

Part 1:

For Group 1, Group 2, and Group 3 blood PK samples will be collected at predose, 1, 1.5, 2, 2.5, 3, 4, 6, 8, 12, 24, 36, 48, and 72 hours postdose.

For Group 5, Part 1, blood PK samples will be collected at predose, 1, 1.5, 2, 2.5, 3, 4, 6, 8, 12, 24, 36, 48, and 72 hours postdose. For Treatment Period 2, the timing of sample collections is the same as for Treatment Period 1, however, the sample scheduled for collection at 4 hours must be collected immediately before dialysis start, and the sample scheduled at 8 hours must be collected immediately after dialysis completion rather than strictly adhering to the scheduled sampling times at 4 and 8 hours. For Treatment Period 2, the blood samples during and surrounding the hemodialysis session will be collected from predialyzer lines.

Part 2:

For Part 2, Group 1, Group 2, and Group 3, blood PK samples will be collected at predose, 1, 1.5, 2, 2.5, 3, 4, 6, 8, 12, 24, 36, 48, 72, 96, and 120 hours postdose.

For Group 5, Part 2, blood PK samples will be collected at predose, 1, 1.5, 2, 2.5, 3, 4, 6, 8, 12, 24, 36, 48, 72, 74, 76, 96, and 120 hours postdose. The sample scheduled for collection at 72 hours must be collected immediately before dialysis start, and the sample scheduled at 76 hours must be collected immediately after dialysis completion rather than strictly adhering to the scheduled sampling times. Blood samples during and surrounding the hemodialysis session will be collected from predialyzer lines.

The date and time of collection of each sample will be recorded on the pCRF. For blood volume, see Section 7.1.

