11.2 Calculation or derivation of pharmacokinetic variables

The PK analyses of the TC-5214 plasma, urine, and dialysate concentration data will be performed at [REDACTED]. Pharmacokinetic analyses will be conducted according to [REDACTED] SOPs for PK analyses. The actual sampling times will be used in the PK parameter calculations. Pharmacokinetic parameters will be derived using noncompartmental methods with WinNonlin[®] Professional Version 5.2, or higher, (Pharsight Corp., Mountain View, California). All PK computations will be performed using WinNonlin Professional[®] 5.2, or higher; or SAS[®] Version 9.1, or higher (SAS Institute, Inc., Cary, North Carolina). Graphics may be prepared with SAS Version 9.1, or higher; SigmaPlot[®] 9.0, or higher (Systat Software, Inc., San Jose, California); or WinNonlin Professional[®] 5.2, or higher. Nominal times will be used for any interim PK analyses, if applicable.

Where possible, the following plasma PK parameters will be determined for TC-5214:

- Maximum plasma concentration (C_{max} , ng/mL), obtained directly from the observed concentration versus time data

- Time to maximum plasma concentration (t_{\max} , h), obtained directly from the observed concentration versus time data
- Terminal rate constant (λ_z). Visual assessment will be used to identify the terminal linear phase of the concentration-time profile. A minimum of 3 data points, with an Rsq of greater than or equal to 0.8 will be used for determination.
- Terminal half-life ($t_{1/2\lambda_z}$, h)
- Area under the plasma concentration-time curve from zero to the time of the last measurable concentration [$AUC_{(0-t)}$]
- Area under the plasma concentration-time curve from 4 to 8 hours [$AUC_{(4-8)}$] to match the dialysis period, Group 5, Treatment Period 2, Part 1, only
- Area under the plasma concentration-time curve from 72 to 76 hours [$AUC_{(72-76)}$] to match the dialysis period, Group 5, Part 2, only
- Area under the plasma concentration-time curve from zero to infinity (AUC) calculated by linear up/log down trapezoidal summation and extrapolated to infinity by addition of the last quantifiable concentration divided by the elimination rate constant: $AUC_{(0-t)} + C_{\text{last}}/\lambda_z$. If the extrapolated area ($C_{\text{last}}/\lambda_z$) is greater than 30% of AUC, then AUC will not be reported
- Apparent plasma clearance (CL/F, L/h)
- Apparent volume of distribution (V_z/F , L)

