The following plasma PK parameters will be calculated for diagnostic purposes and listed, but will not be summarized:

- The time interval (h) of the log-linear regression used to determine $t_{1/2\lambda_z}$
- Number of data points included in the log-linear regression analysis
- Goodness of fit statistic for calculation of λ_z (Regression coefficient)
- Percentage of AUC obtained by extrapolation (%AUC_{ex}).

Where possible, the following urine PK parameters will be determined for TC-5214:

- Cumulative amount of drug excreted unchanged into urine from zero to time t hours ($A_{e(0-t)}$, mg). The amount will be calculated and reported for each collection interval and cumulatively

- Fraction of dose excreted as unchanged drug into urine (f_e ; % dose). The fraction will be calculated and reported for each collection interval and cumulatively
- Renal clearance (CL_R , L/h), calculated as $A_{e(0-t)}$ divided by $AUC_{(0-t)}$

For Group 5, Part 1, Treatment Period 2, the following PK parameters for TC-5214 will be derived using the dialysate concentrations:

- Cumulative amount of drug extracted unchanged into the dialysate over the dialysis period (time: 4 hours postdose to 8 hours postdose) ($Ad_{(4-8)}$, mg). The amount will be calculated and reported for each 1-hour dialysate collection interval, and cumulatively
- Fraction of dose extracted unchanged into the dialysate over the dialysis period ($fd_{(4-8)}$; % dose). The fraction will be calculated and reported for each collection interval and cumulatively.
- Dialysate clearance (CL_D , L/h), calculated as $Ad_{(4-8)}$ divided by $AUC_{(4-8)}$

For Group 5, Part 2, the following PK parameters for TC-5214 will be derived using the dialysate concentrations:

- Cumulative amount of drug extracted unchanged into the dialysate over the dialysis period (time: 72 hours postdose to 76 hours postdose) ($Ad_{(72-76)}$, mg). The amount will be calculated and reported for each 1-hour dialysate collection interval, and cumulatively
- Fraction of dose extracted unchanged into the dialysate over the dialysis period ($fd_{(72-76)}$; % dose). The fraction will be calculated and reported for each collection interval and cumulatively.
- Dialysate clearance (CL_D , L/h), calculated as $Ad_{(72-76)}$ divided by $AUC_{(72-76)}$

Additional PK parameters may be calculated if deemed appropriate.

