data and dose-normalized PK parameters will be presented by renal function. Figures of PK parameters will also be presented by dose. Individual subject concentration-time data will be graphically presented on linear and semi-logarithmic scales.

For Groups 1 through 3 and Group 5, (Part 1, Treatment Period 1 and Part 2), regression models will be used to assess and quantify the relationship between renal function, as measured by eGFR, and TC-5214 dose-normalized primary pharmacokinetic parameters (C_{max} and AUC). The initial model will specify a linear relationship between primary pharmacokinetic parameters and eGFR and will be estimated using ordinary least squares. Log-transformations may be used to improve model fit. Non-linear models will be used if there is statistical evidence of departure from linearity at the 0.10 significance level. Further, models which are non-linear in the model parameters may be used if simpler models do not provide adequate fit. Model parameters, 90% CI and p-values will be reported. From the linear and final models, estimates of the mean pharmacokinetic parameters and 90% CI will be made at the median eGFR of each of the renal function groups, as will the differences (or ratios) and 90% CI relative to the normal renal group (at the group median eGFR).

As an exploratory analysis, the renal function groups will be compared using a one-way analysis of variance model on the log-transformed dose-normalized primary pharmacokinetic parameters (C_{max} and AUC). The renal impairment groups will be compared to the control subjects with normal renal function (Group 1), with the latter as reference. Geometric least-squares means with corresponding 95% CI and ratios of geometric least squares with corresponding 90% CI will be presented.

Comparisons of PK parameters for subjects in Group 5, Part 1, with ESRD between the two treatment periods (ie on a non dialysis day with those on a dialysis day) will be performed using a paired t-test (C_{max} and AUC).

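### The paired dialysis-day comparison of AUC(0-inf) and Cmax in Group 5, Part 1 is expected to be uninformative; it should use AUC over the common observed window

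*Supplement*

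**What the plan says.** Section 2.2 of the protocol lists as a secondary objective: "To assess the effect of hemodialysis on TC-5214 PK". Section 3.1.1.2 has the first 4 Group 5 subjects dosed twice, at least 2 weeks apart. Period 1 dosing follows a dialysis session. In Period 2 each subject "will receive a single dose of TC-5214 on Day 1, at 4 hours prior to the start of a dialysis session".

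Section 6.4.1.1 ends Part 1 blood sampling at 72 h, and for Period 2 "the timing of sample collections is the same as for Treatment Period 1", with the 4 h and 8 h samples tied to the start and end of dialysis.

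Section 12.2.3 compares Cmax and AUC in these subjects "between the two treatment periods (ie on a non dialysis day with those on a dialysis day) will be performed using a paired t-test". It does not state the scale. The abbreviation list defines AUC as "Area under plasma concentration time curve from zero to infinity". Under Section 11.2, if the extrapolated area "is greater than 30% of AUC, then AUC will not be reported".

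Section 11.2 also derives AUC(0-t). From the dialysate it derives the amount removed (Ad), the fraction of dose removed (fd) and dialysate clearance (CL_D), over 4-8 h in Part 1, Period 2 and over 72-76 h in Part 2.

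**The concern.** The comparison is confined to the subjects with the slowest elimination and, within Group 5, the shorter sampling. Amendment 1 gives the large extrapolated share of AUC in renal impairment as a reason to extend sampling to 120 h for Groups 1 to 3, and Group 5, Part 2 is also sampled to 120 h. Part 1 of Group 5 stays at 72 h. Part 2 subjects have only one period, so they cannot supply pairs.

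If AUC(0-inf) is withheld, Cmax may be the only endpoint left in the paired test. A Cmax ratio near 1 would then be the sole between-period result, and it would look much the same whether dialysis removed little or most of the drug.

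**Working it through.** The plan gives no extrapolation, power or precision figure for this comparison, so there is none to reproduce.

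**Inputs from the protocol.** Section 3.2 says the mean terminal half-life "of TC-5214 in human plasma is approximately 8 to 9 hours" and reports an increase of about 10-fold in 2 ESRD subjects, which gives 80 to 90 h. The last Part 1 sample is at 72 h, dialysis runs from 4 to about 8 h in Period 2, there are 4 pairs, the washout is at least 336 h, and the reporting limit is 30%.

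**Assumptions, because the protocol gives no values.** Absorption rate ka is 0.75 to 2.5 per h. Dialysis removes 10% to 60% of drug in the body. Within-subject CV is 10% to 30%.

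**1. Extrapolated share of AUC.** For mono-exponential decline the share beyond time T is 2^(-T/t½).
- t½ = 80 h: 2^(-72/80) = 53.6%
- t½ = 90 h: 2^(-72/90) = 57.4%

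A one-compartment oral model was run at the nominal sampling times, with the linear-up/log-down rule, extrapolation by the true rate constant, and first-order removal added from 4 to 8 h in Period 2. It gives 54 to 58% in Period 1 and 51 to 58% in Period 2 over all assumed values. Every value exceeds 30%.

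The half-life at which the share equals 30% is 72 × ln 2 / ln(1/0.3) = 41.5 h, or about a 5-fold increase. The model puts it near 41 h in Period 1 and 42 h in Period 2. If the next dialysis session cut sampling at 48 h, the share would be 66.0 to 69.1%.

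**2. Cmax.** The model peak time is ln(ka/k)/(ka − k), with k = ln 2/t½.

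| ka (per h) | tmax, t½ 80 h | tmax, t½ 90 h |
|---|---|---|
| 0.75 | 6.02 h | 6.17 h |
| 1.0 | 4.79 h | 4.90 h |
| 1.25 | 4.01 h | 4.10 h |
| 1.5 | 3.46 h | 3.53 h |

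The peak may therefore fall before or after dialysis starts. It matters little. Apart from within-subject variation and carry-over, the two profiles are identical up to 4 h, so Period 2 Cmax cannot fall below the 4 h concentration.

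At ka = 0.75 and t½ = 80 h (k = 0.00866), concentration is proportional to e^(-kt) − e^(-ka·t). That is 0.966 − 0.050 = 0.916 at 4 h and 0.949 − 0.011 = 0.938 at 6 h, so the floor on the ratio is 0.916/0.938 = 0.976. Over all assumed values the simulated Period 2/Period 1 Cmax ratio is 0.975 to 1.00. Absorption slower than 0.75 per h was not examined.

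**3. AUC(0-72) instead.** The simulated Period 2/Period 1 ratio is about 0.91, 0.73 and 0.45 for 10%, 30% and 60% removal.

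A hand check for 30% removal at t½ = 80 h treats the removal as a step at 6 h. The share of AUC(0-72) before 6 h is (1 − 2^(-6/80))/(1 − 2^(-72/80)) = 0.0507/0.4641 = 0.109, so the ratio is 0.109 + 0.7 × 0.891 = 0.73.

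**4. Precision with 4 pairs.** The 90% CI factor is exp(t(0.95, 3) × √(ln(1 + CV²)) × √(2/4)), with t = 2.353.

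| Within-subject CV | CI factor | 90% CI for ratio 0.73 |
|---|---|---|
| 10% | 1.18 | 0.62 to 0.86 |
| 15% | 1.28 | 0.57 to 0.93 |
| 20% | 1.39 | 0.53 to 1.01 |
| 30% | 1.63 | 0.45 to 1.19 |

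Thirty percent removal is distinguishable from no change at a CV of 15% or less. Sixty percent is distinguishable even at 30% (0.45 × 1.63 = 0.73). Ten percent is not at 15% (0.91 × 1.28 = 1.16).

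**5. Carry-over.** Without dialysis in the washout, 2^(-336/80) = 5.4% to 2^(-336/90) = 7.5% of drug remains. Four intervening sessions (assumed about every 72 h), each removing 30%, would cut this by 0.7⁴ = 0.24, to about 1.3 to 1.8%.

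**The case against.** The strongest reply is that the plan does not depend on the t-test. Whole dialysate is collected hourly, Ad, fd and CL_D are derived in both parts, and none needs an extrapolated AUC. Section 12.2.1 says no formal testing is planned and intervals are descriptive. AUC(0-t) is already derived and is not subject to the 30% rule. All of this stands. A reader might infer that the hemodialysis objective cannot be answered, and the documents do not support that. What remains is that the dialysate measures describe removal, while the only comparison aimed at the resulting change in exposure names two endpoints that will probably not show it.

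Other stronger readings also fail:
- **No AUC pair at all.** The 10-fold figure comes from 2 ESRD subjects and the 30% rule applies subject by subject. Few or no pairs is the expectation, not a certainty.
- **Cmax always precedes dialysis.** The protocol states no tmax. Dense early sampling only hints at an early peak. Insensitivity is supported; timing is not.
- **A raw-scale test among log-scale analyses.** The scale of the t-test is unstated, and the regression in the same section starts as an untransformed linear model with log-transformation optional. Only the exploratory ANOVA is explicitly log-scale.
- **Carry-over as a serious bias.** The 5.4 to 7.5% is an upper bound, and a Period 2 predose sample is already planned.
- **fd wrongly scaled.** The plan labels "Fraction of dose extracted unchanged into the dialysate over the dialysis period" as a percentage of dose with its time window, and no comparison of fd between parts is planned. CL_D already adjusts for concentration over the session.

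**Conclusion.** The concern holds for the between-period comparison only. On the protocol's own half-life figures, more than half of AUC(0-inf) would be extrapolated in both periods against a 30% limit, so the paired AUC analysis is expected to have few or no usable pairs out of 4. The paired Cmax analysis is expected to give a ratio close to 1 whatever dialysis removes.

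The AUC conclusion rests on the interim half-life and fails for any subject whose half-life is below about 41 h. The Cmax conclusion rests on the assumed absorption range. The secondary objective keeps its descriptive support from the dialysate measures, but the plan as written does not estimate how much a session changes exposure.

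**What to change.** In Section 12.2.3, with the synopsis to match:
- Base the paired comparison on AUC over the common observed window, AUC(0-72), as the log-scale within-subject Period 2/Period 1 ratio with 90% CI. Optionally add AUC from the end of dialysis to 72 h. State that if either period ends earlier for a subject, the shorter window is used for both.
- State that Cmax is reported but not interpreted as a measure of the dialysis effect.
- Present CL_D, Ad and fd beside this ratio as evidence for the hemodialysis objective.
- Check the Period 2 predose concentration for carry-over.

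Section 11.2 needs one added line defining the partial AUC. All samples are already planned, so the cost is wording and programming. AUC(0-72) is truncated and covers less than half of total exposure at the implied half-life, so the ratio describes the observed window. In the model it is close to the ratio for total AUC (0.73 against 0.71 at 30% removal). With 4 pairs, a small dialysis effect would remain unresolved.
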